8.8. Withdrawals and Loss to Follow-up

Participation is completely voluntary and each subject is free to withdraw from the study at any time. An investigator also has the right to withdraw the subject from the study in the event of reasons concerning the health or well-being of the subject, or in the case of lack of cooperation. Should a subject decide to withdraw for any reason, or should the investigator decide to withdraw the subject, all efforts will be made to complete and report the observations up to the time of withdrawal as thoroughly as possible. A complete final evaluation at the time of the subject's withdrawal must be made and an explanation given of why the subject is withdrawing or being withdrawn from the study.

The reason for and date of withdrawal must be recorded on the subject's End of Study CRF. If the reason for the withdrawal is a device-related or procedure related AE, the event must be reported to the Sponsor and recorded in the CRF.

If the procedure is aborted, the subject does not need to complete the follow-up assessments, unless the subject is converted to surgical repair. The subject's enrollment roster position may not be made available to other subjects.

If a subject dies during the course of the study, the Sponsor will request an autopsy provided the subject authorized an autopsy in the event of death during the course of the study. Autopsy observations should include documentation of condition of body organs and determination of device and/or procedure relationship to death.

All efforts will be made to retain subjects in order to collect data at all the follow-up visits (30 days, 6 months). Due diligence in reaching the subject must be made by:

- Two documented telephone contact attempts, emails, or regular postal mail letters; and
- Certified letter

After the above attempts were made, if no response is obtained, the final evaluation of a given subject will be the last visit at which study-related procedures were performed on that subject. The End of Study CRF page will need to be completed and communication attempts will need to be documented.

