4.7 Missing or Incomplete Data

Every effort will be made to minimize the amount of missing data. Recognizing the difficulty of avoiding some missing data, however, data imputation methods with sensitivity imputation analyses will be carried out. Safety endpoint analysis will include all subjects experiencing at least one component for the safety endpoint or with follow-up to the lower limit of the follow-up window for each time point, i.e., the denominator will be adjusted for missing data. Subjects with missing effectiveness data for target lesions (MLD at the conclusion of atherectomy) will be assumed to have missing data at random and will be imputed by random selection with replacement of data from target lesions with post-atherectomy measurements. The robustness of the multiple imputation outcome will be tested with a tipping point analysis encompassing all possible imputation outcomes.

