5. ENDPOINT ALGORITHMS

5.1 Safety Endpoints

For missing values, an adjustment to the denominator will be made based on the amount of evaluable data for safety-endpoints.

Safety denominator adjustment: For each visit (or reporting time point), the event rate will be calculated as the number of subjects with certain event term over the number of evaluable subjects. The evaluable subjects at each reporting time point include all subjects who are enrolled by the snapshot date and

- 1) Had an event within (on or before) the reporting cutoff days, or
- 2) Had a follow-up at or after the lower limit of the reporting window, or
- 3) The withdrawal consent date/recorded lost-to-follow-up date at or after the lower limit of the reporting window

‘Days to event’ (date of earliest event – date of index procedure) and ‘Days to last contact’ (date of last contact – date of index procedure) are usually used for the determination of the eligibility of the ‘evaluable subject’. The last contact date will be calculated based on the information gathered from all available dates during the follow-ups.

The ‘Reporting Cutoff Days’, ‘Lower limit of the Reporting Window’ and the correspondent visits are as the following:

Visit	Reporting Cutoff Days	Lower Limit of the Reporting Window (days post-index procedure)
1-month	30 days post-index procedure	Days to last contact: 23
6-month	180 days post-index procedure	Days to last contact: 166

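### SAP 5.1 rule 3 can count a subject as free of 30-day MAE on an undefined lost-to-follow-up date alone; SAP 4.7 has no such route

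*SAP*

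**What the plan says.** SAP 4.7 gives two routes into the safety denominator: at least one component event, or being a subject "with follow-up to the lower limit of the follow-up window for each time point". SAP 5.1 restates these as rules 1 and 2 and adds, joined by *or*, rule 3: "The withdrawal consent date/recorded lost-to-follow-up date at or after the lower limit of the reporting window".

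The table in 5.1 labels the 1-month lower limit "Days to last contact: 23". The text above it says that days to event and days to last contact "are usually used for the determination of the eligibility of the" evaluable subject.

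Neither document defines the recorded date of loss. Protocol 8.8 sets out the steps that come first: "Two documented telephone contact attempts, emails, or regular postal mail letters; and" a certified letter. It continues: "After the above attempts were made, if no response is obtained, the final evaluation of a given subject will be the last visit" with study procedures. For withdrawals it is firmer: "The reason for and date of withdrawal must be recorded", and "A complete final evaluation at the time of the subject's withdrawal must be made".

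SAP 4.4 and 4.5 test freedom from 30-day MAE with an exact one-sided 97.5% lower confidence limit (LCL), which must exceed 80%. This is one of two criteria that must both be met.

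**The concern.** Rule 3 matters only for a subject who fails rules 1 and 2, that is, with no recorded event and no follow-up on or after day 23. Such a subject adds one to the denominator and nothing to the event count, and so is analysed as MAE-free without having been observed.

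The route is plausible. The 1-month visit window runs from day 23 to day 37 (SAP 5.2; Protocol Table 6 gives one month ± 1 week). If loss is declared after a missed 1-month visit and the contact attempts in Protocol 8.8, the declaration will normally fall after day 23, even when the subject was last seen at discharge.

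At stake is the denominator of a primary test in a single-arm trial. It may depend on which SAP section the analyst follows and on a date convention that is not written down. No planned analysis clearly covers this. The tipping-point analysis in 4.7 concerns the imputed effectiveness data. The general sentence on sensitivity analyses in 4.7 and the Kaplan-Meier statement in 4.66 do not say how missing 30-day MAE status is handled in the exact test.

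**Working it through.** **Inputs from the SAP.** Goal p0 = 0.80, anticipated freedom from MAE 0.91, one-sided alpha 0.025, exact binomial test, 110 evaluable subjects, 121 enrolled, 10% attrition (SAP 3.3); LCL must exceed 80% (SAP 4.5).

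**Assumptions.** The documents give neither the number of subjects lost (L) nor the share of their events that is seen (s). I take L up to 12 (10% of 121 = 12.1) and s from 0 to 0.9. Lost subjects have the same true MAE rate as the others, and all other subjects are evaluable.

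**1. The plan's own figure.** n = [(1.960·√(0.80·0.20) + 1.282·√(0.91·0.09)) / 0.11]² = 109.4, rounded up to 110; 110 × 1.10 = 121. At n = 110 the exact test needs 97 event-free subjects and has power 88.2%, close to the stated 90%.

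**2. MAE allowed, by denominator.** The smallest r with P[Bin(n, 0.80) ≥ r] ≤ 0.025 gives n − r allowed MAE.

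| Subjects entering only by rule 3 | n under 4.7 | MAE allowed under 4.7 | MAE allowed under 5.1 (n = 121) |
|---|---|---|---|
| 1–2 | 120–119 | 15 | 15 |
| 3–8 | 118–113 | 14 | 15 |
| 9–12 | 112–109 | 13 | 15 |

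**3. Results that change** (Clopper-Pearson one-sided 97.5% LCL).

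- 3 entries, 15 MAE: 106/121, LCL 80.38%, pass; 103/118, LCL 79.90%, fail.
- 12 entries, 14 MAE: 107/121, LCL 81.35%, pass; 95/109, LCL 79.39%, fail.
- 12 entries, 15 MAE: 106/121, LCL 80.38%, pass; 94/109, LCL 78.32%, fail.

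At the planned 9% MAE rate, the chance of exactly 15 MAE among the 118 other subjects is P[Bin(118, 0.09) = 15] = 4.5%.

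**4. Type I error under literal rule 3.** P[Bin(121 − L, 0.80) + Bin(L, 1 − 0.20s) ≥ 106].

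| Share of lost subjects' events seen (s) | L = 12 | 2.5% exceeded from |
|---|---|---|
| 0 | 6.1% | L = 3 (2.65%; L = 2 gives 2.41%) |
| 0.25 | 4.7% | L = 4 (2.66%) |
| 0.50 | 3.6% | L = 5 (2.54%) |
| 0.75 | 2.7% | L = 10 (2.55%) |
| 0.90 | 2.2% | not exceeded up to L = 12 |

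With complete data on 121 subjects it is 2.0%.

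**5. Tipping point.** On n = 121 the test fails at 16 MAE (105/121, LCL 79.42%). With 12 missing, 13 MAE in 109 passes (96/109, LCL 80.47%), but the full cohort fails if 3 or more of the 12 had an MAE (13 + 3 = 16). With 10 observed MAE, 6 or more are needed.

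**The case against.** **Last contact governs.** The sentence on last contact and the label of the day-23 limit can be read as controlling all three rules. A subject last contacted at discharge would then not be evaluable. This is a fair reading, but the text says only that last contact is usually used, and on this reading the lost-to-follow-up part of rule 3 would be redundant. It leaves 5.1 ambiguous.

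**SAP 4.7 is a summary and 5.1 its algorithm.** Follow-up to the lower limit might mean being still on study at day 23. That is possible, but a reader of 4.7 alone would not admit a subject without contact.

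**Sites may record the last visit.** Protocol 8.8 makes it the final evaluation, and no passage says that the declaration date is used instead. This stands: the harm depends on an unstated convention.

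**The group is small.** Rule 2 has no upper limit, so anyone seen at a later unscheduled or 6-month visit is already evaluable. The 10% attrition is not stated to be loss to follow-up only. Both points stand, and 12 is an unlikely ceiling.

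**Early events are captured.** AEs are assessed at treatment and discharge (Protocol 8.3, 8.4 and Table 6), so early events of lost subjects enter by rule 1. This stands and favours the rows of the type I table with a higher share seen.

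**Stronger readings.** A reader might infer that the plan definitely counts unobserved subjects as successes, or that the safety test runs at about 6% type I error. The documents support neither. The first needs a particular date convention. The second also needs 12 such subjects with none of their events seen. Nor does the point carry over fully to withdrawals, for which Protocol 8.8 requires a recorded date and a final evaluation, although rule 3 does not itself require that the evaluation took place.

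**Conclusion.** The concern holds as a defect of definition in a primary analysis. Read literally, rule 3 opens a route into the 30-day denominator that 4.7 lacks, through a date that nobody has defined. If that date is when loss was declared, the error favours the device; if it is the last visit, the effect is close to nil.

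The probable size is small, and it bears on the result only near the pass limit: no change with one or two entries, a change at exactly 15 MAE with three to eight, and at 14 or 15 MAE with nine to twelve. Whether the 2.5% level is exceeded depends on the assumed number lost and share of events seen. This should be fixed because the two sections can give different denominators and the correction is mostly wording. Confidence is medium, since the site convention is unknown.

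**What to change.** 1. In SAP 5.1, delete the lost-to-follow-up route in rule 3, or define that date as the last documented contact with AE assessment. Remove the word *usually*, and align 5.1 with 4.7.
2. Add a tipping-point and worst-case table for missing 30-day MAE status, laid out as in step 5 of the working.

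The effort is SAP wording and one table. There is also a statistical cost. A last-contact rule keeps the known events of lost subjects and drops their event-free peers, so it leans against the device. Resetting the critical value for each resulting n, with 12 lost, power at 91% freedom from MAE is 88.8%, 84.8% or 80.3% if none, half or all of their events are seen (92.3% with complete data on 121). Type I error is then 1.9%, 1.0% or 0.5%. With 6 lost, power is about 91%, 89% or 87%. The table in item 2 is needed for this reason as well: it shows the result under both favourable and unfavourable assumptions about the missing subjects.

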5.2 Effectiveness Endpoints

Patency effectiveness endpoints (site-reported endpoints) include the endpoints that are determined by site assessment (DUS or angiography), such as the significant stenosis/occlusion measured by DUS or angiography as well as consideration of the clinical endpoint – TVR. Such site-reported endpoints rely on the actual evaluable assessment. If the scheduled assessment is not completed or the data is not evaluable (i.e., not readable, or non-diagnostic), it will be treated as missing value and will be excluded from the analysis.

The significant stenosis component for the patency endpoints (primary patency and primary-assisted patency) is determined by a qualified angiogram diameter stenosis (DS) $\geq 50\%$ and $<100\%$ evaluated by the site or qualified DUS evaluated as DUS category ‘50-99%’ that is evaluated by the site-reported DUS. The occluded component of primary and secondary patency endpoints is determined by a qualified angiogram DS=100% or qualified DUS evaluated as ‘occluded’. Either significant stenosis or occlusion will be considered failure of primary patency.

Data will be used for subjects who have an evaluable (readable or diagnostic) scheduled or unscheduled DUS or angiographic assessment (site-reported imaging assessments) that will be based on reporting windows described below. To minimize the missing assessment at 1 and 6-month visits, analysis windows provided below will be utilized.

Given that angiography is a more precise visualization of the vessel than DUS, in cases where both angiography and DUS are available at the same assessment and they provide different conclusions then angiography will be preferentially used in the algorithm.

Step 1. For convention, the imaging visits use the following reporting windows. The study day used in the window definitions is calculated as “assessment date” minus “Index procedure date”:

Study Visit	Target Day	Compliance Reporting Windows	Analysis Reporting Windows
Index Procedure	Day 0	N/A	N/A
Discharge	Discharge	N/A	1-discharge
30-days	Day 30	Study Day 23 – 37	15-60
6-month	Day 180	Study Day 166 – 194	61-210

These reporting windows serve 2 primary functions:

- 1) Allow for the calculation of compliance to imaging follow-up for each visit – compliance reporting window ranges.
- 2) Provide the analysis reporting windows for patency endpoints at key follow-up time points.

Step 2. If the scheduled assessment is not completed or is not evaluable (i.e. not readable or non-diagnostic), this assessment will be censored (or excluded from proceeding to the next step).

Step 3. If a visit has multiple DUS or angiographic assessments, the following hierarchical criteria will be used to identify the appropriate assessment for that visit:

- Choose the one that has a positive observation(s) – i.e. significant reduction of blood flow, etc.; if more than one assessment contains at least one positive observation, the earliest assessment will be used;
- If none of the assessments has positive observations, choose the one that is the closest to the scheduled visit date

Step 4. If a visit has both DUS assessment and angiographic assessment, the following hierarchical criteria will be used to identify the appropriate assessment for that visit to use in the analysis:

- If there are multiple DUS assessments or multiple angiographic assessments that are slotted in the same visit window, please refer to step 3 to select one non-missing assessment for DUS and/or angiography separately. Please refer to the following table for the assessment and outcome determination

DUS assessment	Angiographic assessment	Final selected assessment	Final selected assessment outcome
Success	Failure	Angiography	Failure

Success	Success	Choose the one that is the closest to or earlier than the scheduled visit date	Success
Success	Missing	DUS	Success
Failure	Failure	Choose the one that is the closest to or earlier than the scheduled visit date	Failure
Failure	Success	Angiography	Success
Failure	Missing	DUS	Failure
Missing	Failure	Angiography	Failure
Missing	Success	Angiography	Success
Missing	Missing	N/A	Missing

As stated previously and shown in the hierarchy above, in cases where both angiography and DUS are available at the same assessment and they provide different conclusions then angiography will be preferentially used.

The step-by-step description of the above hierarchical criteria in determining the 1 and 6-month site assessments is as follows:

- 1) Remove the assessments with value of 'N/A' or 'missing'. If the assessment result is N/A or missing, then delete (e.g., set the value to 'missing');
- 2) Data will be used for subjects who have an evaluable (readable) scheduled or unscheduled DUS or scheduled or unscheduled angiography. Failure of patency can occur at any time post-procedure. Choose the first occurrence of angiography for failure. If no angiography failure, then choose the first occurrence of DUS failure. If there are no failures, but there are success(es) then choose the last successful occurrence of angiography and if no angiography then use the last successful occurrence of DUS. If there are no DUS or angiography assessments, then set the value to 'missing'.

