7.5. Secondary Endpoints

The following secondary endpoints will be studied:

1. Change in percent stenosis after treatment with Revolution™ Peripheral Atherectomy System, determined after atherectomy and prior to other adjunctive therapies, as measured by the angiographic core laboratory
2. Procedural success as defined by target lesion residual stenosis of $< 30\%$ at the conclusion of the index procedure, after atherectomy and any adjunctive endovascular treatment, as measured by the angiographic core laboratory;
3. Assessment of the individual components of the primary safety endpoint (MAE); including all-cause mortality, major target limb amputation, clinically significant distal embolization, major target vessel perforation requiring surgical or endovascular repair, and clinically-driven TLR, measured through 30 days and at 6 months.;
4. Minor unplanned target limb amputation rate through 30 days and 6 months;
5. Myocardial infarction through 30 days and 6 months;
6. Incidence of TVR through 30 days and 6 months;

^g Technical success is defined on the post-atherectomy angiogram, prior to adjunctive therapy with balloon angioplasty, stent deployment, or any other intervention.

^h Shan, G. C. Ma. Efficient tests for one sample correlated binary data with applications. *Stat Methods Appl*, 23:175-188, 2014.

7. Frequency of angiographic procedural distal embolization (symptomatic) in the target limb as confirmed angiographically by the core laboratory;
8. Primary patency of the target lesion at 30 days and 6 months, determined by duplex ultrasound or angiography;
9. Primary-assisted patency of the target lesion at 30 days and 6 months, determined by duplex ultrasound or angiography.
10. Secondary patency of the target lesion at 30 days and 6 months, determined by duplex ultrasound or angiography.

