8.4. Hospital Discharge Assessment

Subjects will be evaluated during the time after procedure completion and prior to hospital release. The following information will be collected on the Hospital Discharge CRF:

- Time spent in ICU (hours) and hospital (days)
- Examination of incision site and assessment of healing
- AE observation
- Replacement fluids (blood products) administered post procedure

^j Ankle- or toe-brachial indices and duplex ultrasound/angiography are only required at unscheduled visits if the reason for the unscheduled visit was related to target limb symptoms.

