13.6. Core Reference Laboratory

A central core reference laboratory will independently evaluate duplex ultrasound and angiographic imaging data collected at participating institutions. All protocol-specified imaging studies must be sent to the Core Laboratory for evaluation. Refer to the Core Lab Manual for details about the identified laboratory and instructions for submitting data.

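### Patency is scored from site readings, and the SAP gives no role to the core-laboratory readings that the protocol calls for

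*SAP*

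**What the plan says.** SAP section 5.2 names the reader for patency: "Patency effectiveness endpoints (site-reported endpoints) include the endpoints that are determined by site assessment (DUS or angiography". The same section takes the significant-stenosis component from an angiogram read at the site, or from a duplex category "that is evaluated by the site-reported DUS". The step-by-step algorithm that follows, and the composite tables in SAP 5.21 to 5.23, keep to site-reported imaging. This is a consistent rule and not a slip of wording.

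Protocol section 13.6 sets up a second reading of the same material: "A central core reference laboratory will independently evaluate duplex ultrasound and angiographic imaging data collected at participating institutions", and "All protocol-specified imaging studies must be sent to the Core Laboratory for evaluation". Duplex or angiography at 1 month and 6 months is in the schedule of assessments (Protocol Table 6), so those scans are protocol-specified.

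The protocol's own endpoint wording names no reader for patency. Item 8 of Protocol 7.5 reads "Primary patency of the target lesion at 30 days and 6 months, determined by duplex ultrasound or angiography", and items 9 and 10 follow the same pattern.

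Unscheduled scans also count. The SAP states: "Data will be used for subjects who have an evaluable (readable or diagnostic) scheduled or unscheduled DUS or angiographic assessment". A footnote to Protocol Table 6 limits when such scans are mandatory: "duplex ultrasound/angiography are only required at unscheduled visits if the reason for the unscheduled visit was related to target limb symptoms".

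**The concern.** Two readings of the scheduled follow-up scans should exist, one from the treating institution and one from an independent laboratory. The SAP uses only the first and does not say why.

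Two things are at stake. The first is independence: in a single-arm study the institution that delivered the treatment grades the result, and there is no concurrent control arm in which the same reader error would also occur. The second is uniformity: up to 18 sites sort duplex scans into a 50 to 99 percent category or an occluded category, and SAP 5.2 gives no velocity cut-off for doing so. By contrast, the definition of clinically driven TLR in SAP 2.1 states a peak systolic velocity ratio above 2.4. One laboratory would apply one standard to all sites.

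A misread scan can also carry forward. Under SAP 5.21 a failure of primary patency is kept at every later time point. Under SAP 5.22 and 5.23 a success on primary patency is automatically a success on the other two, so a failure missed on primary patency is missed on all three.

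**Working it through.** The plan states no figure on this point, so the check is a comparison of texts, followed by an illustration under assumed values.

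**Step 1. Who reads which imaging endpoint.**

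| Endpoint | Reader named in protocol | Reader used in SAP |
|---|---|---|
| Technical success (primary) | Core laboratory (5.2, 7.3) | Core laboratory (2.2, 4.3) |
| Change in percent stenosis | Core laboratory (7.5, item 1) | Core laboratory |
| Procedural success | Core laboratory (7.5, item 2) | Core laboratory |
| Angiographic distal embolization | Core laboratory (7.5, item 7) | Core laboratory |
| Primary, primary-assisted and secondary patency | None named (7.5, items 8 to 10) | Site (5.2, 5.21 to 5.23) |

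Patency is the exception among the imaging endpoints.

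**Step 2. Does the plan expect the two readers to differ?** Yes, at least for anatomy. Protocol 6.5 and 9.3 treat site and core-laboratory measurements as separate quantities, and the core-laboratory vessel diameter decides which lesions enter the per-protocol set.

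**Step 3. Which scans should have a core-laboratory reading?** Scheduled 1-month and 6-month scans are covered by Protocol 13.6. Unscheduled imaging is required only for target-limb symptoms, and Protocol 8.7 otherwise leaves assessments at unscheduled visits to the investigator. The SAP uses those scans too, so some scans that decide patency may have no core-laboratory reading.

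**Step 4. What part of patency is exposed?** Only the imaging component. Clinically driven TLR also sets primary patency to failure (SAP 5.21), and it is adjudicated by the CEC as part of the 30-day primary safety endpoint.

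**Step 5. Illustration of size.** The documents give no patency rate and no rate of site versus core-laboratory disagreement, so both inputs are assumptions. Let L be the true share losing patency and m the share of those failures that sites miss, with no errors in the other direction. Overstatement of patency = L × m.

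| True loss L | m = 10% | m = 20% | m = 30% |
|---|---|---|---|
| 10% | 1 point | 2 points | 3 points |
| 20% | 2 points | 4 points | 6 points |
| 30% | 3 points | 6 points | 9 points |

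**Step 6. Direction.** Let f be the share of truly patent subjects that sites call failed. The net overstatement is L × m − (1 − L) × f, which is zero when f = L × m / (1 − L). With L = 20%:

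- m = 10%: f = 0.02 / 0.80 = 2.5%
- m = 30%: f = 0.06 / 0.80 = 7.5%

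Above these values of f, site reading understates patency. Modest over-calling is therefore enough to reverse the sign.

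**The case against.** The strongest reply is that no rule is broken. The protocol leaves the reader for patency open, section 13.6 says that images are evaluated and not that the evaluation defines patency, and the SAP fills the gap. That stands as far as it goes: this is not a breach of an endpoint definition. But it does not make the site rule equally good, because the core laboratory is the named reader for the other imaging endpoints and the SAP offers no reason for the exception.

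A second reply is that the SAP already limits lenient reading. Among several scans of one type, Step 3 selects the positive one, and failures carry forward. This is true, but neither rule corrects a single misread scan.

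Third, the cost may be higher than it looks. Protocol 15.2 mentions only angiograms in connection with the core laboratory, the endpoint text speaks of an angiographic core laboratory, and the details are left to a Core Lab Manual that is not among the documents. This stands as a condition on the fix: a reader might infer that usable duplex readings are already available and paid for, but the documents do not show that.

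Two further inferences are tempting and go too far. One is that the core laboratory has a reading of every scan used; section 13.6 covers protocol-specified imaging only. The other is that unblinded operators grade their own work against a blinded laboratory. The documents do not say who at a site reads the scans, and in a single-arm study the core laboratory also knows that every subject received the device. Its advantage is independence and uniform reading, not masking.

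**Conclusion.** The point holds as a risk that can be avoided at low cost. Three secondary endpoints rest on site readings, while the protocol provides for independent readings of the same scheduled scans, and the SAP neither uses those readings nor explains why.

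A reader might infer that reported patency will be biased upward. The documents do not support this, because they fix neither the size nor the direction of any bias. The 1 to 9 point range holds only under the assumed loss rates and miss rates and with no false failures.

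The consequence is limited. Patency has no performance goal and no hypothesis test. Study success depends only on the two primary endpoints (Protocol 7.4, SAP 4.5), and the primary effectiveness endpoint is read by the core laboratory. The change is worth making, but the study's success test does not depend on it.

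**What to change.** In SAP 5.2 and 5.21 to 5.23:

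1. Use the core-laboratory reading as the source for stenosis and occlusion wherever one exists. Settle the reader for each scan before Steps 2 to 4 are applied.
2. Use the site reading only for scans that the core laboratory never read, for example discretionary unscheduled scans. Flag these and report how many there are.
3. Treat a scan that is non-diagnostic at the core laboratory as non-evaluable under Step 2. Do not revert to the site reading.
4. Report site-read patency as a sensitivity analysis, together with site and core-laboratory agreement.

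If the sponsor keeps site reading as the main source, the SAP should at least give the reason and add core-laboratory patency as the sensitivity analysis.

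The cost is SAP wording and a change of data source. A few scans will become non-evaluable, and a small number of fallback site readings will remain, so the endpoint will not have a single reader throughout. That the cost is low assumes that the core laboratory reads follow-up duplex as Protocol 13.6 states; this should be confirmed against the Core Lab Manual before the text is changed.
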